### 7.2. Participant Discontinuation/Withdrawal From the Study

A participant may withdraw from the study at any time at his/her own request. Reasons for stopping study participation include the following:

- Refused further follow-up
- Lost to follow-up
- Death

- Study terminated by sponsor

At the time of discontinuing from the study, if possible, an early discontinuation visit should be conducted. See the [SoA](#) for assessments to be collected at the time of study discontinuation and follow-up and for any further evaluations that need to be completed.

Participants should be questioned regarding their reason for withdrawal.

### **7.2.1. Withdrawal of Consent**

Participants who request to discontinue receipt of study intervention will remain in the study and must continue to be followed for protocol-specified procedures. The only exception to this is when a participant specifically withdraws consent for any further assessments or contact with his or her or persons previously authorized by the participant to provide this information. Participants should notify the investigator of the decision to withdraw consent from future follow-up. Participants should be questioned regarding their reason for withdrawal. The investigator must inform the TIMI Hotline of the withdrawal of consent. The withdrawal of consent should be explained in detail in the medical records by the investigator, as to whether the participant is only stopping further receipt of study intervention or withdrawing from study procedures and/or posttreatment study follow-up, and entered on the appropriate CRF page. At the time of withdrawal from the study, if possible, an Early Termination/Discontinuation visit should be conducted. See the [SoA](#) for assessments to be collected at the time of study withdrawal.

If a participant withdraws consent from the study, he/she may request destruction of any remaining samples taken and not tested, and the investigator must document any such requests in the site study records and notify the sponsor accordingly.

If the participant withdraws consent for disclosure of future information, no further evaluations should be performed and no additional data should be collected. The sponsor may retain and continue to use any data collected before such withdrawal of consent.

Lack of completion of all or any of the withdrawal/early termination procedures will not be viewed as protocol deviations so long as the participant's safety was preserved.

Publicly available information should be used to determine vital status (whether the participant is alive or dead) only as appropriately directed in accordance with local law.

### **7.3. Lost to Follow-up**

To prevent participants being lost to follow-up, their contact details, including next of kin contacts, should be collected initially and updated regularly by the site staff or representative. The investigator should educate the participant on the importance of contact with the investigator throughout the study.

Repeated attempts will be made to locate and obtain pertinent medical information for participants who are initially lost to follow-up. A participant will be classified as lost to follow-up only if he/she has failed to return for the required study visits and his/her vital

status remains unknown at the end of the study despite multiple attempts to contact him/her via telephone, fax, email, certified letter, or through patient locator agencies (if allowed by national regulation). Where permissible by local law, the ICD will include language to grant the option to employ outside companies to assist in obtaining updated contact information or ascertainment of vital status of lost participants using publicly available source.

## **8. STUDY ASSESSMENTS AND PROCEDURES**

The investigator (or an appropriate delegate at the investigator site) must obtain a signed and dated ICD before performing any study-specific procedures.

Study procedures and their timing are summarized in the [SoA](#). Protocol waivers or exemptions are not allowed.

Safety issues should be discussed with the sponsor immediately upon occurrence or awareness to determine whether the participant should continue or discontinue study intervention.

Adherence to the study design requirements, including those specified in the [SoA](#), is essential and required for study conduct.

All screening evaluations must be completed and reviewed to confirm that potential participants meet all eligibility criteria. The investigator will maintain a screening log to record details of all participants screened and to confirm eligibility or record reasons for screening failure, as applicable.

Every effort should be made to ensure that protocol-required tests and procedures are completed as described. However, it is anticipated that from time to time there may be circumstances outside the control of the investigator that may make it unfeasible to perform the test. In these cases, the investigator must take all steps necessary to ensure the safety and well-being of the participant. When a protocol-required test cannot be performed, the investigator will document the reason for the missed test and any corrective and preventive actions that he or she has taken to ensure that required processes are adhered to as soon as possible. The study team must be informed of these incidents in a timely manner.

For samples being collected and shipped, detailed collection, processing, storage, and shipment instructions and contact information will be provided to the investigator site prior to initiation of the study.

The total blood sampling volume for individual participants in this study is approximately 250 mL. The actual collection times of blood sampling may change. Additional blood samples may be taken for safety assessments at times specified by Pfizer, provided the total volume taken during the study does not exceed 550 mL during any period of 60 consecutive days.

## 8.1. Efficacy Assessments

### 8.1.1. Lipids

Blood samples for measurement of TC, direct LDL-C, HDL-C, TG, and direct VLDL-C should be collected from participants in a fasted state (see [Section 5.3.2](#)) as indicated in the [SoA](#); non-HDL-C will be calculated as TC – HDL-C.

Lipid results from Day 1 onward will not be reported to study sites or other blinded personnel until the study has been unblinded (see [Section 8.2.7](#) for potential exception).

### 8.1.2. Lipoproteins and FFA

Blood samples for measurement of Lp(a), ApoB, ApoB-48, ApoB-100, ApoC-III, ApoA-I, and FFA should be collected from participants in a fasted state (see [Section 5.3.2](#)) as indicated in the [SoA](#).

Lipoprotein and FFA results from Day 1 onward will not be reported to study sites or other blinded personnel until the study has been unblinded.

### 8.1.3. hsCRP

Blood samples for measurement of hsCRP should be collected from participants in a fasted state (see [Section 5.3.2](#)) as indicated in the [SoA](#).

hsCRP results will not be reported to study sites or other blinded personnel until the study has been unblinded.

## 8.2. Safety Assessments

Planned time points for all safety assessments are provided in the [SoA](#). Unscheduled clinical laboratory measurements may be obtained at any time during the study to assess any perceived safety issues.

### 8.2.1. MRI-PDFF Assessments

At scheduled visits (refer to the [SoA](#)), liver fat will be assessed via MRI using the PDFF acquisition method. Each assessment will require the participants to be in a supine position in the confined space of the MRI scanner for approximately 25 minutes with the image acquisition undertaken following a fast (except water) of  $\geq 4$  hours, and as much as practically possible, at the same time ( $\pm 2$  hours) of the day relative to assessment at Screening.

Across the study sites selected for this study, the sponsor-identified central imaging vendor will train the imaging facility staff on the MRI-PDFF acquisition protocol, on just-in-time review of the acquired images for assessment of images being deemed evaluable, and on transfer (preferably electronically) of the images to the sponsor-identified central imaging vendor for analysis and quantification of liver fat. **Only the staff members at the imaging facility who are trained by the sponsor-identified central imaging vendor are permitted to acquire images**; however in rare/limited situations, exceptions may be granted with

written approval of the sponsor. Complete details on the MRI-PDFF acquisition protocol, determination of quality of images, and transmission of data to sponsor-identified central imaging vendor will be provided in an Imaging Manual provided to the sites prior to the start of the study.

As much as practically possible, analysis of the MRI-PDFF images acquired at baseline and Week 24 will be undertaken by a single reviewer at the sponsor-identified central imaging vendor who will be blinded to individual participant's clinical data, as well as randomization assignment. MRI-PDFF images will be blinded to study sites, blinded personnel, participants, and sponsor until the study has been unblinded.

#### **8.2.1.1. Management of Incidental Findings**

An incidental finding is one unknown to the participant that has potential health or reproductive importance, which is discovered unexpectedly in the course of a research study but is unrelated to the purpose and beyond the aims of the study. The images will be reviewed by a sponsor-identified central review facility. The purpose of this review is to evaluate images for the amount of fat in the liver. Central image review is not a complete medical review of the participant. If, during the central review process, an unexpected observation is identified and this finding could, in the opinion of the central reviewer, have a significant health or reproductive consequence, this finding may be shared with the study sponsor for disclosure to the PI. All follow-up testing and final diagnosis will be left to the discretion of the medical professionals at the site or those with an existing physician-participant relationship. The PI will be responsible for reporting any AEs identified from incidental findings as described in the AE reporting section. Identification of such incidental findings during the central review process should not be expected, and the site maintains responsibility for performing a general safety review of all images as per site protocols.

#### **8.2.2. Physical Examinations**

Physical examination will be performed at Screening.

A complete physical examination will include, at a minimum, assessments of the cardiovascular, respiratory, gastrointestinal, and neurological systems.

Height will be measured and recorded at Screening, and weight will be measured and recorded at Screening, Day 1, Day 169, and Early Termination/Discontinuation, if applicable (see [SoA](#)).

Investigators should pay special attention to clinical signs related to previous serious illnesses.

#### **8.2.3. Vital Signs**

Single seated blood pressure and pulse rate will be assessed at times specified in the [SoA](#) with a completely automated device. Manual techniques will be used only if an automated device is not available.

Blood pressure and pulse rate measurements should be preceded by at least 5 minutes of rest for the participant in a quiet setting without distractions (eg, television, cell phones).

#### 8.2.4. Electrocardiograms

Standard 12-lead ECG utilizing limb leads (with 10 second rhythm strip) should be collected at times specified in the [SoA](#) section of this protocol using an ECG machine that automatically calculates the heart rate and measures PR, QT, and QTc intervals, and QRS complex. Alternative lead placement methodology using torso leads (eg, Mason-Likar) should not be done given the potential risk of discrepancies with ECGs acquired using standard limb lead placement.

- All *scheduled* 12-lead ECGs should be performed with the participant in a supine position;
- ECG values of potential clinical concern are listed in [Appendix 7](#).
  - If a machine-read QTc value is prolonged, as defined in [Appendix 7](#), repeat measurements may not be necessary if a qualified physician's interpretation determines that the QTc values are in the acceptable range;
    - Assessment of whether prolonged QTc interval meets criteria as defined in [Appendix 7](#), must assess QTc interval using *only* the Fridericia's correction (ie, QTcF) *either* as reported by the 12-lead ECG machine *or* QTcF derived using sponsor-provided tool and reported QT and RR intervals.
- In some cases, it may be appropriate to repeat abnormal 12-lead ECG to rule out improper lead placement as contributing to the ECG abnormality; *as much as practically possible*, it is important that leads be placed in the same positions each time in order to achieve precise ECG recordings.

#### 8.2.5. Clinical Safety Laboratory Assessments

See [Appendix 2](#) for the list of clinical safety laboratory tests to be performed and the [SoA](#) for the timing and frequency. Safety assessments include blood chemistry, hematology, urinalysis, UACR, PT, aPTT, INR, HbA1c, and pregnancy test. All protocol-required laboratory assessments, as defined in [Appendix 2](#), must be conducted in accordance with the laboratory manual and the [SoA](#). *Note: safety laboratory results from Week 1 visit should be reviewed by the investigator prior to Week 2 dosing for participants dosing Q2W and prior to Week 4 dosing for participants dosing Q4W.* Unscheduled clinical laboratory measurements may be obtained at any time during the study to assess any perceived safety issues.

The investigator must review the laboratory report, document this review, and record any clinically relevant changes occurring during the study in the AE section of the CRF. Clinically significant abnormal laboratory findings are those which are not associated with the underlying disease under study, unless judged by the investigator to be more severe than expected for the participant's condition.

All laboratory tests with values considered clinically significantly abnormal during participation in the study or within 12 weeks after the last dose of study intervention should be repeated until the values return to normal or baseline or are no longer considered clinically significant by the investigator or TIMI Hotline.

If such values do not return to normal/baseline within a period of time judged reasonable by the investigator, the etiology should be identified as much as possible and the sponsor notified.

See [Appendix 6](#) for suggested actions and follow-up assessments in the event of potential drug-induced liver injury.

### **8.2.6. Pregnancy Testing**

Pregnancy tests may be urine or serum tests, but must have a sensitivity of at least 25 mIU/mL. Pregnancy tests will be performed in WOCBP at the times listed in the [SoA](#). Following a negative pregnancy test result at Screening, appropriate contraception must be commenced and a second negative pregnancy test result will be required at the baseline visit prior the participant's receiving the study intervention. Pregnancy tests will also be done whenever 1 menstrual cycle is missed during the active treatment period (or when potential pregnancy is otherwise suspected) and at the end of the study. Pregnancy tests may also be repeated if requested by IRBs/ ECs or if required by local regulations. If a urine test cannot be confirmed as negative (eg, an ambiguous result), a serum pregnancy test is required. In such cases, the participant must be excluded and discontinued from study intervention if the serum pregnancy result is positive.

### **8.2.7. Potential Severe Cases of Hypertriglyceridemia**

In certain circumstances, unblinding of TG results may occur during the study. In the event a participant's fasting (see [Section 5.3.2](#)) TG is >1000 mg/dL, as reported by the sponsor-identified central laboratory, the investigator and sponsor will receive an alert from the laboratory along with the unblinded TG level. The investigator is to repeat the TG test via the central laboratory, ideally within 7 days of receipt. The investigator should counsel the participant on diet and lifestyle factors to improve the TG level prior to the repeat measurement. For participants with a confirmed TG value of >1000 mg/dL, the investigator will again counsel the participant on diet and lifestyle, and the investigator can titrate the statin dose (if applicable) or can add a medication to lower TG at the investigator's discretion. In only these circumstances (confirmed TG value of >1000 mg/dL), the prohibited TG lowering medications in [Section 6.5.1](#) are not applicable.

### **8.3. Adverse Events and Serious Adverse Events**

The definitions of an AE and an SAE can be found in [Appendix 3](#).

The definitions of device-related safety events (ADEs and SADEs) can be found in [Appendix 8](#). Device deficiencies are covered in [Section 8.3.8](#).

AEs will be reported by the participant (or, when appropriate, by a caregiver, surrogate, or the participant's legally authorized representative).

The investigator and any qualified designees are responsible for detecting, documenting, and recording events that meet the definition of an AE or SAE and remain responsible to pursue and obtain adequate information both to determine the outcome and to assess whether the event meets the criteria for classification as an SAE (see [Appendix 3](#)) or caused the participant to discontinue the study intervention (see [Section 7.1](#)).

Each participant will be questioned about the occurrence of AEs in a nonleading manner.

In addition, the investigator may be requested by Pfizer Safety to obtain specific follow-up information in an expedited fashion.

### **8.3.1. Time Period and Frequency for Collecting AE and SAE Information**

The time period for actively eliciting and collecting AEs and SAEs (“active collection period”) for each participant begins from the time the participant provides informed consent, which is obtained before the participant’s participation in the study (ie, before undergoing any study-related procedure and/or receiving study intervention), through and including a minimum of 12 weeks, except as indicated below, after the last administration of the study intervention.

Follow-up by the investigator continues throughout and after the active collection period and until the AE or SAE or its sequelae resolve or stabilize at a level acceptable to the investigator and Pfizer concurs with that assessment.

For participants who are screen failures, the active collection period ends when screen failure status is determined.

If the participant withdraws from the study and also withdraws consent for the collection of future information, the active collection period ends when consent is withdrawn.

If a participant definitively discontinues or temporarily discontinues study intervention because of an AE or SAE, the AE or SAE must be recorded on the CRF and the SAE reported using the CT SAE Report Form.

Investigators are not obligated to actively seek AEs or SAEs after the participant has concluded study participation. However, if the investigator learns of any SAE, including a death, at any time after a participant has completed the study, and he/she considers the event to be reasonably related to the study intervention, the investigator must promptly report the SAE to Pfizer using the CT SAE Report Form.

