### 1.3. Schedule of Activities (SoA)

The SoA table provides an overview of the protocol visits and procedures. Refer to the [STUDY ASSESSMENTS AND PROCEDURES](#) section of the protocol for detailed information on each procedure and assessment required for compliance with the protocol. The investigator may schedule visits (unplanned visits) in addition to those listed in the SoA table, in order to conduct evaluations or assessments required to protect the well-being of the participant. In the event of a health care crisis, pandemic, or other emergency, some of the assessments may be performed via home health visits or other ways after discussion with the sponsor. See [Appendix 13](#) for alternative measures that may be allowed during a public emergency, such as COVID-19.

Visit Identifier a Abbreviations used in this table may be found in Appendix 14 .	Screening b (Days -28 to -1)			Day 1	Day 8	Day 15	Day 29	Day 43	Day 57	Day 85	Day 113 Interim Analysis Time Point	Day 141	Day 169	Follow-up (+12 weeks after last dose) c,f	Early Termination/ Discontinuation g
	Visit 1 c,d	Visit 2	Visit 3												
Week	-4 to -1			0	1	2	4	6	8	12	16	20	24	32 or 34	
Month	-1						1		2	3	4	5	6	8	
Visit Window (Days)					±1	±1	±2	±2	±2	±3	±3	±3	±3	±7	
Informed consent	X														
Medical history	X														
Inclusion/Exclusion Criteria	X			X											
Physical examination	X														
Vital signs (seated blood pressure and pulse rate)	X			X							X		X		X
Weight	X			X									X		X
Height	X														
Provide contact card to participant	X														
Dispense diary and instruct participant on use				X h											
Laboratory															
Hematology	X			X	X i	X	X	X	X	X	X	X	X	X	X
Blood chemistry	X			X	X i	X	X	X	X	X	X	X	X	X	X
Lipid panel and ApoB j	X			X			X		X	X	X	X	X	X	X
Extended lipoprotein panel and FFA k				X									X		X
ANGPTL3 l				X			X		X	X	X	X	X		X
HbA1c	X			X									X	X	X

Visit Identifier a Abbreviations used in this table may be found in Appendix 14 .	Screening b (Days -28 to -1)			Day 1	Day 8	Day 15	Day 29	Day 43	Day 57	Day 85	Day 113 Interim Analysis Time Point	Day 141	Day 169	Follow-up (+12 weeks after last dose) c,f	Early Termination/Discontinuation g
	Visit 1 c,d	Visit 2	Visit 3												

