Week	-4 to -1			0	1	2	4	6	8	12	16	20	24	32 or 34	
Month	-1						1		2	3	4	5	6	8	
Visit Window (Days)					±1	±1	±2	±2	±2	±3	±3	±3	±3	±7	
Urinalysis	X			X	X i	X	X	X	X	X	X	X	X	X	X
Urine albumin to creatinine ratio	X			X	X i	X	X	X	X	X	X	X	X	X	X
FSH (women, if applicable)	X														
Pregnancy test m	X			X		X	X	X	X	X	X	X	X	X	X
Plasma PK										X n	X n		X o		X
hsCRP				X									X		X
PT, aPTT, INR				X	X i	X	X	X	X	X	X	X	X	X	X
Anti-vupanorsen antibodies (ADA)				X p						X p	X p	X p	X p	X	X
Banked Biospecimen Samples Prep B1.5 (plasma), B2.5 (serum), M4 (urine) q				X									X o		X
Pfizer Prep D1 Banked Biospecimen(s) q				X											
Contraception check				X	X	X	X	X	X	X	X	X	X	X	X
12-Lead ECG	X												X o		X
MRI-PDF r			X										X o,s		X
Randomization				X											
IRT interaction	X	X		X		X t	X	X t	X	X	X	X			X
Study intervention															
Placebo-injection instruction and training		X													
Q2W u,v				X		X i	X	X	X	X	X	X			
Q4W u				X		X i			X	X	X	X			
Review diary to assess treatment compliance										X	X	X	X		X

Visit Identifier a Abbreviations used in this table may be found in Appendix 14 .	Screening b (Days -28 to -1)			Day 1	Day 8	Day 15	Day 29	Day 43	Day 57	Day 85	Day 113 Interim Analysis Time Point	Day 141	Day 169	Follow-up (+12 weeks after last dose) e,f	Early Termination/ Discontinuation g
	Visit 1 c,d	Visit 2	Visit 3												
Week	-4 to -1			0	1	2	4	6	8	12	16	20	24	32 or 34	
Month	-1						1		2	3	4	5	6	8	
Visit Window (Days)					±1	±1	±2	±2	±2	±3	±3	±3	±3	±7	
Prior and concomitant treatment(s)	X			X	X	X	X	X	X	X	X	X	X	X	X
Serious and nonserious adverse event monitoring	X	X	X	X	X	X	X	X	X	X	X	X	X	X	X

Visit Identifier a Abbreviations used in this table may be found in Appendix 14 .	Screening b (Days -28 to -1)			Day 1	Day 8	Day 15	Day 29	Day 43	Day 57	Day 85	Day 113 Interim Analysis Time Point	Day 141	Day 169	Follow-up (+12 weeks after last dose) e,f	Early Termination/ Discontinuation g
	Visit 1 c,d	Visit 2	Visit 3												
Week	-4 to -1			0	1	2	4	6	8	12	16	20	24	32 or 34	

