Month	-1						1		2	3	4	5	6	8	
Visit Window (Days)					±1	±1	±2	±2	±2	±3	±3	±3	±3	±7	

- a. Day relative to start of study intervention (Day 1).
- b. Screening Period is a maximum of 28 days. Complete all inclusion/exclusion procedures and assessments denoted at Screening Visit 1; placebo injection training may be performed at Screening Visit 1 or Screening Visit 2. After participant has otherwise qualified for the study, including review of lipid and clinical laboratory results and completion of successful placebo training injections, perform MRI-PDFF at Screening Visit 3 or any time prior to randomization.
- c. If participants are not fasted for lipid panel and ApoB collection, perform other Screening activities and have participants return fasted for these tests.
- d. Screening Visit 1 activities should be completed within 7 days.
- e. Occurs 12 weeks after last dose: Week 32 for participants assigned to Q4W regimen or Week 34 for participants assigned to Q2W regimen.
- f. For participants who discontinue the study after Week 24, perform Follow-up procedures; do not perform Early Termination/Discontinuation procedures.
- g. For participants who discontinue study intervention or discontinue the study prior to Week 24, the procedures should be performed. Early Termination/Discontinuation procedures to be performed *as soon as practically possible* after decision to stop study intervention but participants should stay in study with continuation of scheduled visits unless participant withdraws consent from further study participation.
- h. Diary to be dispensed only to participants assigned to Q2W regimen.
- i. Laboratory results from Week 1 visit should be reviewed by the investigator prior to Week 2 dosing for participants dosing Q2W and prior to Week 4 dosing for participants dosing Q4W.
- j. Lipid panel and ApoB should be obtained with participants in a fasted state ([Section 5.3.2](#)). Lipid panel includes non-HDL-C, TG, direct LDL-C, total cholesterol, HDL-C, direct VLDL-C.
- k. Extended lipoprotein panel and FFA should be obtained with participants in a fasted state ([Section 5.3.2](#)). Extended lipoprotein panel includes Lp(a), ApoB-48, ApoB-100, ApoC-III, ApoA-I.
- l. ANGPTL3 should be obtained with participants in a fasted state ([Section 5.3.2](#) and [Section 8.6](#)).

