- m. For WOCBP. Perform serum pregnancy test at Screening. Perform urine pregnancy test prior to dosing at visits on Week 0, Week 2 through Week 24, Follow-up, and Early Termination/Discontinuation (if applicable).
- n. PK sample collected with participants in a fasted state ([Section 5.3.2](#)) at trough (prior to dosing with study intervention) and 2 to 4 hours after administration.
- o. Do not perform assessment/procedure at Day 169 for participants who continued scheduled visits after stopping study intervention and completed Early Termination/Discontinuation assessments/procedures.
- p. ADA samples to be collected prior to dosing with study intervention.
- q. If not collected on the designated collection day, collect at the next available time point when biospecimens are being collected in conjunction with a participant visit.
- r. Assessment to be performed, following ≥4-hour fast, at site (as part of site visit) or separate visit(s) to Imaging facility (see [Section 5.3.2](#)).
- s. Attempts to be made to stay within ±2-hour window of the time when MRI-PDFF was performed at Screening.
- t. Dispense study intervention only to participants assigned to Q2W regimen for home dosing.
- u. For each site visit, perform all indicated procedures and assessments prior to participant self-injection (or caregiver administering injection).
- v. Dosing at home for participants in the Q2W regimens will occur on Weeks 10, 14, 18, and 22; the window for each scheduled dosing day is ±2 days. Study intervention will be dispensed at the prior visit for these doses.

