#### **4.4. End of Study Definition**

A participant is considered to have completed the study if he/she has completed all phases of the study including follow-up visit.

The end of the study is defined as the date of the last visit of the last participant in the study.

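### Protocol Section 8.3.1 states at least 12 weeks of active AE/SAE collection after the last dose, but the Schedule of Activities allows the final contact at 11.0 weeks

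*Protocol*

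**What the plan says.** Four parts of the protocol bear on this.

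- **Section 8.3.1** sets the length of active AE and SAE collection: from consent "through and including a minimum of 12 weeks, except as indicated below, after the last administration of the study intervention". The limits that follow concern screen failures and participants who withdraw consent to further data collection.
- **Section 1.3 (SoA), footnote e**, places the Follow-up visit: "Occurs 12 weeks after last dose: Week 32 for participants assigned to Q4W regimen or Week 34 for participants assigned to Q2W regimen". The column heading also counts the visit from the last dose. The window row gives this column ±7 days.
- **Section 1.3, row "Serious and nonserious adverse event monitoring"**, is marked at every visit, including Week 24 and Follow-up. Nothing is scheduled after Follow-up.
- **Sections 4.4 and 8.3.1** fix what happens next. Section 4.4: "A participant is considered to have completed the study if he/she has completed all phases of the study including follow-up visit". Section 8.3.1: "Investigators are not obligated to actively seek AEs or SAEs after the participant has concluded study participation".

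The last dose has a window of its own. For Q4W participants it is given at the Week 20 visit (±3 days). For Q2W participants it is given at home at Week 22, where "the window for each scheduled dosing day is ±2 days".

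**The concern.** Section 8.3.1 sets a floor, while the SoA sets a target equal to that floor with a tolerance on both sides. A visit in the early half of the window is on schedule, completes the study and ends the duty to seek events, yet it falls before the stated minimum. Neither limit listed in Section 8.3.1 covers an early visit.

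Safety and tolerability are stated objectives, and treatment-emergent events are counted throughout the study. Section 2.2.4.1 gives a terminal half-life of 3 to 5 weeks, so a week of follow-up is about a fifth to a third of a half-life. What is at stake is whether the stated length of post-dose AE collection is true for participants who kept to the schedule.

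**Working it through.** **Inputs**

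- Stated minimum: 12 × 7 = 84 days (Protocol 8.3.1).
- Nominal last dose: Week 20 = Day 141 (Q4W); Week 22 = Day 155 (Q2W) (SoA and footnote v).
- Follow-up: Week 32 or Week 34 (footnote e), ±7 days (window row).
- Last-dose windows: ±3 days (Q4W) and ±2 days (Q2W).

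**Step 1: reproduce the plan's own figure.** Nominal last dose plus 84 days:

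- Q4W: 141 + 84 = Day 225 = Week 32.
- Q2W: 155 + 84 = Day 239 = Week 34.

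Both match footnote e and the target days in SAP Appendix 2.1. The nominal interval equals the minimum, with no slack.

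**Step 2: earliest in-window visit, counted from the last dose** (column heading and footnote e). 84 − 7 = 77 days = 11.0 weeks in both regimens. The shortfall is 7 days, or 7/84 = 8.3%.

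**Step 3: earliest in-window visit, counted from Day 1.** Footnote a describes SoA days as "Day relative to start of study intervention (Day 1"). On that reading, a late last dose and an early visit add up:

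- Q4W: (225 − 7) − (141 + 3) = 218 − 144 = 74 days = 10.6 weeks; shortfall 10 days.
- Q2W: (239 − 7) − (155 + 2) = 232 − 157 = 75 days = 10.7 weeks; shortfall 9 days.

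**Step 4: share of completers below 84 days.** The documents give no distribution of visit timing, so these are assumptions.

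- Visit day uniform over −7 to +7, counted from the last dose: 7/15 = 46.7%.
- Visit and dose days both uniform, counted from Day 1: Q4W has 15 × 7 = 105 combinations, of which 7 give exactly 84 days, so (105 − 7)/2 = 49 fall short, and 49/105 = 46.7%. Q2W has 15 × 5 = 75, so (75 − 5)/2 = 35, and 35/75 = 46.7%.
- Visit day triangular, peaked on target (weights 8 − |k|, total 64, of which 28 lie before target): 28/64 = 43.8%.
- Limits: 0% if every visit is on or after day 84; 100% if every visit is early.

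**Step 5: other contacts.** Week 24 (Day 169) also follows the last dose, by 169 − 141 = 28 days (Q4W) or 169 − 155 = 14 days (Q2W), and it includes AE monitoring. It does not help with the floor, because it comes well before day 84.

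**Step 6: would a 0 to +7 day window fit the SAP?** With the last dose given in its window:

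| | Earliest visit | Latest visit | SAP Appendix 2.1 window |
|---|---|---|---|
| Q4W | 138 + 84 = Day 222 | 144 + 84 + 7 = Day 235 | Day 211 to 238 |
| Q2W | 153 + 84 = Day 237 | 157 + 84 + 7 = Day 248 | Day 225 to 252 |

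Both fit. A final dose after Day 147 (Q4W, 238 − 91) or Day 161 (Q2W, 252 − 91) could lead to a visit beyond the SAP window.

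**The case against.** The strongest reply is that the two rules can be met together. A visit on days 84 to 91 satisfies both, sites must follow Section 8.3.1 as well as the SoA, and unplanned visits are permitted for participants' well-being. Section 4.4 asks for all phases to be completed, the design calls for a 12-week safety follow-up, and related SAEs learned of later must still be reported. This shows that a careful site can comply. It does not remove the mismatch, because the SoA expressly permits days 77 to 83, and no call or visit is scheduled to fill the gap.

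Other objections limit the point, and they stand:

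- A reader might take 10.6 weeks as the plain lower limit. That needs the Day 1 count, a Q4W last dose 3 days late and a visit 7 days early. The column heading and footnote e favour 77 days.
- A reader might infer that about half of completers fall short. No visit-timing data support this; the figure follows from assuming symmetric timing.
- A reader might call Follow-up the only contact after treatment. Week 24 is one too.
- A reader might say that the final laboratory sample breaks the same promise. Section 8.3.1 concerns AE and SAE collection and sets no minimum for laboratory sampling.
- A reader might expect an AE analysis to fail. The SAP's definition of treatment-emergent events (Section 3.5.1) has no post-dose cutoff, so no planned analysis depends on day 84. Nor does any passage say that the report will claim at least 12 weeks for every participant.

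**Conclusion.** The inconsistency is real and minor. A final visit centred on 84 days with a symmetric ±7-day window does not guarantee a minimum of 84 days, and nothing scheduled later makes up the difference. The largest shortfall is 7 days on the last-dose count, or 10 days (Q4W) and 9 days (Q2W) on the Day 1 count. These figures assume that the last planned dose is taken in its window and that the visit is on schedule.

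The share affected is unknown. It is 43.8% to 46.7% under the timing assumptions shown, and 0% to 100% without them. The documents do not support a claim that AE percentages would be materially wrong, and the Week 24 primary endpoint is unaffected. What needs correcting is the stated length of follow-up and the unclear starting point of the window.

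**What to change.** Reconcile Section 8.3.1 with the SoA in the next amendment.

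1. State in the SoA that the Follow-up window is counted from the actual last dose. The heading and footnote e already point that way; saying so removes the Day 1 reading.
2. Then take one of two routes:
   - let the window open no earlier than day 84, for example 0 to +7 days; or
   - keep ±7 days and restate Section 8.3.1 as approximately 12 weeks, with the true lower bound of 77 days on the last-dose count.

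The first route cuts the scheduling window from 15 days to 8. It needs no SAP change when the last dose is given in window; the sponsor should check how later final doses are assigned. The second leaves scheduling alone but states a slightly less favourable follow-up figure. Neither adds a visit, a procedure or a participant. The choice is the sponsor's.
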